5.1 Children with Cancer (n=50)

Participants in this group will be children with a confirmed cancer diagnosis, such as leukemia, lymphoma, or solid tumors, who are currently hospitalized for treatment at the inpatient oncology wards of Hong Kong Children's Hospital. Eligible participants must be actively receiving cancer-directed therapy (e.g., chemotherapy, radiation) during their hospital stay. Inclusion criteria require that participants, or their parents or legal guardians as proxies, can provide accurate reports about sleep patterns, either through self-assessment or observation, ensuring reliable data collection. This group will capture the acute impact of cancer treatment and hospitalization on sleep, a critical focus of the study.

5.2 Children with Other Chronic Illnesses (n=50)

This group will comprise children diagnosed with chronic conditions other than cancer, such as asthma, type 1 diabetes, or chronic kidney disease, recruited from the cardiac, nephrology, and mixed wards of Hong Kong Children's Hospital. These illnesses are selected for their known potential to disrupt sleep—e.g., nocturnal asthma symptoms or glucose instability—while differing in pathophysiology from cancer. Participants must be under active management for their condition and currently hospitalized, but must not have a history of primary sleep disorders (e.g., narcolepsy, obstructive sleep apnea) unrelated to their chronic illness. This criterion ensures that observed sleep disturbances are attributable to the chronic condition rather than pre-existing sleep pathology.

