4.4.3 Healthy Children

Healthy children are expected to demonstrate the highest sleep quality among the three groups, with results showing near-optimal sleep duration and efficiency. Reported data are anticipated to reflect low levels of sleep disturbances, with the majority of children scoring below the clinical threshold on the PSQI. These findings will provide a baseline for understanding how chronic illnesses and hospitalization affect sleep outcomes.

5. Study Population

This study will enroll Chinese children aged 6 to 18 years, divided into three distinct groups based on their health status: children with cancer, children with other chronic illnesses, and healthy children. A total sample size of 150 participants (50 per group) will be targeted to ensure adequate statistical power for comparative analyses. Recruitment will occur at Hong Kong Children's Hospital or the cancer and chronic illness groups, and healthy children will be recruited from healthy siblings of participants or the healthy children of hospital staff with specific inclusion and exclusion criteria applied to each group to maintain homogeneity and minimize confounding variables.

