5.3 Healthy Children (n=50)

The healthy control group will be of adequate sample size. These include siblings of pediatric patients (both oncology and non-oncology wards), and children of hospital staff (e.g., nurses, administrative personnel). Inclusion criteria require no history of chronic illness, psychiatric disorders, or known sleep conditions. Parental consent and child assent will be obtained for all participants.

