5.4 Exclusion Criteria

Across all three groups, children will be excluded if they are not Chinese and are in intensive care units. Children who exhibit severe cognitive impairments that preclude accurate reporting of sleep experiences, either by themselves or their parents or legal guardians, will be excluded. Additionally, participants with neurological conditions known to independently affect sleep, such as epilepsy or cerebral palsy, will be excluded to avoid confounding the primary relationship between chronic illness and sleep disturbances. The use of sedative medications unrelated to the participant's primary condition (e.g., for behavioral management rather than cancer treatment) will also disqualify participants, as these could artificially alter sleep patterns and obscure study outcomes. These exclusion criteria ensure that sleep disturbances observed are primarily linked to the participants' health status rather than extraneous factors.

6. Procedure

Participants will be enrolled following informed parental consent and, for children under 18, age-appropriate assent, as detailed in the ethical approval section. Recruitment will occur at Hong Kong Children's Hospital for the cancer and chronic illness groups, while healthy controls will be recruited from siblings of sick children or children of hospital staff. Once enrolled, parents or legal guardians and participants will receive the demographics, the Chinese version of PSQI and PedsQL surveys in paper format, depending on preference, with instructions provided by trained research staff. Completing the questionnaires is estimated to take approximately 15-20 minutes. For hospitalized children (the cancer and chronic illness groups), surveys will be completed during their inpatient stay to capture real-time sleep experiences, and the study team will collect completed questionnaires on the same day. Healthy children can return their questionnaires via their parents/legal guardians, one extra visit may be required by the parents/legal guardians.

7. Statistical Analysis

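### A history of unrelated primary sleep disorder bars a child from the chronic-illness group but not from the cancer group, so the objective 2 comparison can shift, probably slightly, toward the stated hypothesis

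*Protocol*

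**What the plan says.** Eligibility is set group by group in Protocol section 5, whose opening paragraph describes "specific inclusion and exclusion criteria applied to each group to maintain homogeneity and minimize confounding variables".

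- **Chronic illness (5.2):** children "must not have a history of primary sleep disorders (e.g., narcolepsy, obstructive sleep apnea) unrelated to their chronic illness". The reason follows: "This criterion ensures that observed sleep disturbances are attributable to the chronic condition rather than pre-existing sleep pathology".
- **Healthy children (5.3):** "Inclusion criteria require no history of chronic illness, psychiatric disorders, or known sleep conditions".
- **Cancer (5.1):** a confirmed diagnosis, a current inpatient stay, and reliable reporting of sleep by child or parent. On treatment, "Eligible participants must be actively receiving cancer-directed therapy (e.g., chemotherapy, radiation) during their hospital stay". Sleep disorders are not mentioned.
- **All groups (5.4):** two exclusions come near the point. One states that "participants with neurological conditions known to independently affect sleep, such as epilepsy or cerebral palsy, will be excluded". The other disqualifies for "The use of sedative medications unrelated to the participant's primary condition". Primary sleep disorders are not named.

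Section 2 (objective 2) compares sleep in children with cancer with that in the other two groups. Section 4.4.1 predicts that the cancer group will sleep worst. Section 4.3.1 makes the global PSQI score the primary endpoint, and section 7 compares it across groups by one-way ANOVA. The variables listed in section 4.3.3 include hypnotic use but not sleep-disorder history.

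**The concern.** The two inpatient groups are screened differently for a cause of poor sleep that neither illness produced. The reason given in 5.2, to separate the effect of the illness from earlier sleep pathology, applies just as well to cancer, and the protocol gives no ground for exempting that group. The difference also works against the purpose stated for the common list in 5.4 ("These exclusion criteria ensure that sleep disturbances observed are primarily linked to the" children's health status) and for the group criteria in section 5.

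If affected children enter the cancer group and score worse on the PSQI than other cancer inpatients, the cancer mean rises for a reason unrelated to cancer. The shift favours the 4.4.1 hypothesis, on the primary endpoint. Because the history is not listed for collection, a later analysis plan could neither adjust for it nor test how sensitive the result is to it.

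Two limits apply. The stricter rule for healthy children is defensible, since they serve as a benchmark; the inconsistency lies between the two patient groups. Objective 1, prevalence and nature of sleep problems in children with cancer, is not biased, because these children belong to the population it describes.

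**Working it through.** **Does 5.4 close the gap?** Take a sleep disorder unrelated to the main illness.

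| History | Chronic illness | Cancer |
|---|---|---|
| Narcolepsy | excluded by 5.2 | possibly excluded by the neurological criterion in 5.4 |
| Sleep disorder treated with a sedative unrelated to the main illness | excluded by 5.2 | excluded by 5.4 |
| Obstructive sleep apnoea, no such sedative | excluded by 5.2 | eligible |

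The gap is narrowed but not closed; the last row is one of the two examples that 5.2 itself gives.

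**How large could the shift be?** The protocol states no figure to reproduce. It supplies only 50 children per group, the one-way ANOVA and the 0.05 threshold. The share affected, their excess PSQI over other cancer inpatients, and the SD are assumptions, so a range is shown.

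Shift in the cancer mean: b = share × excess.

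ANOVA with only the cancer mean shifted: the group means are (b, 0, 0) around a grand mean of b/3, so the squared deviations sum to b²(4/9 + 1/9 + 1/9) = (2/3)b². The noncentrality is 50 × (2/3) × b² / SD², referred to F with 2 and 147 degrees of freedom. At SD 3:

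| Share | Excess | b (points) | b in SD | Noncentrality | Rejection with no true difference |
|---|---|---|---|---|---|
| 2% | 2 | 0.04 | 0.013 | 0.0059 | 5.0% |
| 5% | 3 | 0.15 | 0.05 | 0.083 | 5.6% |
| 10% | 3 | 0.30 | 0.10 | 0.333 | 7.5% |

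For b = 0.15, rejection is 5.9% at SD 2.5 and 5.3% at SD 4. Simulating the affected children as a mixture (40,000 runs, SD 3) gives 5.1%, 5.6% and 7.3% for the three rows.

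**The direct contrast.** As an illustration only, since the protocol plans no such test, take a two-group t test of cancer against chronic illness with 98 degrees of freedom. The standard error is 3 × √(2/50) = 0.60, so b = 0.15 is 0.15/0.60 = a quarter of a standard error. False findings of cancer worse rise from 2.5% to 4.3%, false findings in the other direction fall from 2.5% to 1.4%, and total two-sided rejection is 5.7%.

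**Scale.** With 50 per group, the pairwise difference detectable with 80% power at two-sided 0.05 is (1.96 + 0.84) × √(2/50) = 0.56 SD. The middle case is 0.05/0.56, about 9% of that.

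**After the change.** With the same criterion in both patient groups, the shift from this source is zero.

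**The case against.** The strongest reply is that the effect is too small to matter. The middle case is about 9% of the detectable difference, and at the low end the ANOVA error rate does not move. All three inputs are assumed, and they may be generous: a history can include resolved or treated disorders with little present excess, and section 4.4.1 already expects most cancer inpatients to score above the poor-sleep threshold. The ANOVA error rates suppose that all three groups sleep equally well, which the protocol does not expect. The 4.3% is one tail of an unplanned test. Group-specific criteria are announced in section 5, so a difference is not in itself a contradiction. Excluding these children would also narrow objective 1, and someone must judge whether a disorder is related to the illness.

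Most of this stands as a limit on size. The one-sided figure should be read with its two-sided total of 5.7%, and the 0.05 SD shift is the more relevant number for the contrast between the patient groups. None of it supplies a reason for the difference between 5.1 and 5.2. Section 5 announces group-specific criteria in order to reduce confounding, and this difference adds some. The judgement of relatedness is already required by 5.2. The narrowing of objective 1 is real but slight, and the second option below avoids it.

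**Conclusion.** The concern holds. The cancer group is the only one without a sleep-disorder criterion, the protocol's own reason for the criterion applies to it equally, and neither the listed variables nor the planned ANOVA can correct for the difference. The shift runs toward the stated hypothesis, provided that affected children enrol and sleep worse than other cancer inpatients.

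Its size is probably small and cannot be derived from the protocol: 0.04 to 0.30 PSQI points over the assumed range, with ANOVA rejection of 5.0% to 7.5% when there is no true difference. It does not threaten the study, but it is avoidable, runs in one direction and would be invisible in the data as planned. It should be fixed.

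**What to change.** Move the 5.2 criterion into 5.4 for both patient groups: no history of a primary sleep disorder unrelated to the cancer or the chronic illness. Sleep problems arising from the illness or its treatment stay eligible, and the stricter rule in 5.3 stays for healthy children. Add to 4.3.3, in all three groups, history of a diagnosed sleep disorder: yes/no, type, and whether it is related to the illness or its treatment.

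If the sponsor prefers to keep such children with cancer for objective 1, record the history and run the objective 2 comparison without children who have an unrelated disorder.

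The cost is a one-line amendment, one screening question and one added data field. A few children with cancer become ineligible or are left out of the comparison; under exclusion, the population described for objective 1 narrows slightly.

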5.3 Healthy Children (n=50)

The healthy control group will be of adequate sample size. These include siblings of pediatric patients (both oncology and non-oncology wards), and children of hospital staff (e.g., nurses, administrative personnel). Inclusion criteria require no history of chronic illness, psychiatric disorders, or known sleep conditions. Parental consent and child assent will be obtained for all participants.

5.4 Exclusion Criteria

Across all three groups, children will be excluded if they are not Chinese and are in intensive care units. Children who exhibit severe cognitive impairments that preclude accurate reporting of sleep experiences, either by themselves or their parents or legal guardians, will be excluded. Additionally, participants with neurological conditions known to independently affect sleep, such as epilepsy or cerebral palsy, will be excluded to avoid confounding the primary relationship between chronic illness and sleep disturbances. The use of sedative medications unrelated to the participant's primary condition (e.g., for behavioral management rather than cancer treatment) will also disqualify participants, as these could artificially alter sleep patterns and obscure study outcomes. These exclusion criteria ensure that sleep disturbances observed are primarily linked to the participants' health status rather than extraneous factors.

6. Procedure

Participants will be enrolled following informed parental consent and, for children under 18, age-appropriate assent, as detailed in the ethical approval section. Recruitment will occur at Hong Kong Children's Hospital for the cancer and chronic illness groups, while healthy controls will be recruited from siblings of sick children or children of hospital staff. Once enrolled, parents or legal guardians and participants will receive the demographics, the Chinese version of PSQI and PedsQL surveys in paper format, depending on preference, with instructions provided by trained research staff. Completing the questionnaires is estimated to take approximately 15-20 minutes. For hospitalized children (the cancer and chronic illness groups), surveys will be completed during their inpatient stay to capture real-time sleep experiences, and the study team will collect completed questionnaires on the same day. Healthy children can return their questionnaires via their parents/legal guardians, one extra visit may be required by the parents/legal guardians.

7. Statistical Analysis

Data will be analyzed using SPSS (version 29), a powerful statistical software package designed for clinical research. Descriptive statistics such as means, standard deviations, and frequencies, will summarize demographic characteristics (e.g., age, gender distribution), as well as PSQI global and component scores, and PedsQL total and subscale scores for each group. To compare sleep quality and health-related quality of life across the three groups, a one-way analysis of variance (ANOVA) will be used for continuous variables (e.g., PSQI global score, sleep duration, PedsQL physical functioning score). For secondary analyses, multiple linear regression will examine the relationships between sleep quality (PSQI score) and potential predictors (e.g., type of cancer treatment, pain levels) while adjusting for confounding factors such as age, gender, and socioeconomic status (SES). Pearson or Spearman correlations will be utilized to assess the relationships between PSQI and PedsQL scores, helping to evaluate the impact of sleep disturbances on health-related quality of life. A p-value of less than 0.05 will indicate statistical significance, and effect sizes (e.g., eta-squared) will be reported to quantify the magnitude of differences.

8. Parental Consent and Children's Assent

Ensuring the ethical participation of children in this study requires a dual approach, involving obtaining informed consent from parents or legal guardians and, where appropriate, obtaining assent from the children themselves.

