1.2 Comparison with Healthy Children and Other Chronic Illnesses

In contrast, healthy children generally experience more consistent and undisturbed sleep accentuates how chronic illnesses combined with hospitalization damage children's sleep quality. Children with other chronic illnesses also encounter sleep difficulties yet their reasons for these issues differ from those diagnosed with cancer. For instance, the condition of asthma triggers nighttime awakenings because of wheezing and coughing, while diabetic patients experience disrupted sleep due to fluctuating glucose levels (Adavadkar et al., 2022; Meltzer & Mindell, 2017). These conditions cause sleep interference but patients tend to experience less psychological and physical distress from cancer which leads to milder overall sleep issues.

2. Study Objectives

The objectives of this study are threefold:

- 1) To assess the prevalence and nature of sleep disturbances in children with cancer.
- 2) To compare sleep disturbances in children with cancer to those in healthy children and children with other chronic diseases.
- 3) To identify potential factors contributing to sleep disturbances in paediatric patients.

3. Study Significance

This study contributes to the comprehension of pediatric sleep disturbances by carefully evaluating sleep disruptions among three groups: children with cancer, children with other chronic illnesses, and healthy children. The data generated from this study provides vital information for developing targeted therapies specific to population groups with linked sleep disturbance factors. By pinpointing specific contributors, such as hospital environment, medication effects, or pain, the research will lay the groundwork for targeted interventions. These could include reducing nighttime disruptions, refining pain management, or designing sleep-friendly hospital settings. Furthermore, integrating tools like the Chinese version of PSQI into routine care could enable early detection and management of sleep issues, mitigating long-term risks like cognitive and emotional deficits

Beyond oncology, the study's comparison with children who have other chronic illnesses will reveal how different conditions uniquely disrupt sleep, guiding tailored strategies for diverse patient groups. The healthy control group will establish a benchmark for normal sleep, highlighting the extent of disruption caused by chronic illness and elevating sleep as a priority in pediatric care.

4. Methods

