4.3 Key Variables

4.3.1 Primary Outcome Variable

Sleep quality, measured by the global PSQI score, will be the primary endpoint. This encompasses the seven component scores (e.g., sleep duration, latency, efficiency), providing a holistic assessment of sleep health. A global score >5 will classify participants as having poor sleep quality, enabling prevalence comparisons across groups.

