4.3.3 Demographic Variables

To control for potential confounding effects on sleep patterns and access to healthcare resources, the following demographic and clinical variables will be collected: age (in years), gender, socioeconomic status (SES), disease type, disease status, and use of hypnotics (yes/no). SES will be assessed through parental education (categorized as primary or below, junior secondary, senior secondary, or university/college and above). For children with cancer, disease type (e.g., leukemia, lymphoma, brain tumor, bone tumor, or others) and disease status (e.g., stage 1-4, recurrence, years since diagnosis, treatment type such as chemotherapy, radiotherapy, surgery, immunotherapy, transplant, or combination) will be recorded. For children with other chronic illnesses, disease type (e.g., asthma, type 1 diabetes, chronic kidney disease) will be noted. These factors may influence sleep outcomes, e.g., older children may report greater daytime dysfunction, or lower parental education level may limit access to supportive care, necessitating adjustment in statistical analyses to isolate the effects of chronic illness on sleep quality.

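### The primary three-group comparison is fixed as an unadjusted one-way ANOVA, although the protocol itself says adjustment is needed to isolate the illness effect

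*Protocol*

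**What the plan says.** Section 4.3.1 names the endpoint: "Sleep quality, measured by the global PSQI score, will be the primary endpoint". Objective 2 in Section 2 is "To compare sleep disturbances in children with cancer to those in healthy children and children with other chronic diseases".

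Section 4.3.3 says why age, gender, SES (measured by parental education) and several clinical variables are recorded: "To control for potential confounding effects on sleep patterns and access to healthcare resources". It gives age and parental education as its examples and ends by describing these factors as "necessitating adjustment in statistical analyses to isolate the effects of chronic illness on sleep quality".

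Section 7 then fixes the group comparison: "a one-way analysis of variance (ANOVA) will be used for continuous variables (e.g., PSQI global score, sleep duration, PedsQL physical functioning score". Adjustment appears only under secondary analyses, in a multiple regression of PSQI on "potential predictors (e.g., type of cancer treatment, pain levels) while adjusting for confounding factors such as age, gender, and socioeconomic status (SES".

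On comparability, Section 5 describes recruitment "with specific inclusion and exclusion criteria applied to each group to maintain homogeneity and minimize confounding variables". Section 5.3 draws the healthy controls from "siblings of pediatric patients (both oncology and non-oncology wards), and children of hospital staff", with no fixed mix.

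**The concern.** One section says that the illness effect on sleep cannot be isolated without adjustment. Another names, for that same effect on the primary endpoint, a test that cannot adjust.

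The design does not supply the missing balance. Eligibility leaves age free between 6 and 18 years and does not touch parental education. Sibling controls narrow the parental-education gap, because they share parents with patients. Children of hospital staff can widen it.

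At stake is the reading of the main result. A difference between cancer and healthy children could partly reflect older patients or differently educated parents, and a real difference could be masked by an imbalance in the other direction.

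**Working it through.** **The text.** Isolating the effect of chronic illness is a contrast between groups, which is Objective 2 on the primary endpoint. Section 7 gives one test for that contrast, with group as its only factor. Study group is not among the example predictors of the secondary regression, and one of those examples, cancer treatment type, does not exist for two of the three groups.

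**Inputs from the protocol.** 50 children per group, three groups, significance at 0.05, ages 6 to 18. There is no figure of the plan's own to reproduce: it gives no PSQI standard deviation, effect size or group distribution.

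**Assumed inputs.** Residual SD 3 PSQI points. Parents with university education: 40% for patients, 40% for siblings, 80% for staff children. PSQI 1 to 2 points lower with university-educated parents. PSQI 0.2 to 0.3 points higher per year of age. Age SD 3.2 years, clipped to 6–18.

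**Bias.** Bias in the unadjusted difference = covariate effect × difference in covariate mean or proportion.

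- Half the controls siblings: proportion 0.5 × 0.40 + 0.5 × 0.80 = 0.60. Bias = (0.60 − 0.40) × 1 to 2 = 0.20 to 0.40 points.
- Staff children only: (0.80 − 0.40) × 1 to 2 = 0.40 to 0.80 points.
- Controls 2 years younger: 2 × 0.2 to 0.3 = 0.4 to 0.6 points before clipping.

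**False-positive rate by noncentral F.** If both patient groups are shifted by d against healthy, λ = 50 × (2/3)d² / 3², tested on 2 and 147 df:

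| d | λ | P(reject) |
|---|---|---|
| 0.2 | 0.148 | 6.1% |
| 0.4 | 0.593 | 9.6% |
| 0.8 | 2.370 | 25.6% |

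**False-positive rate by simulation** (8,000 runs per scenario, no true group effect):

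| Scenario | One-way ANOVA |
|---|---|
| No imbalance | 4.8% |
| Half siblings, education effect 1–2 points | 6.4%–8.8% |
| Staff children only, education effect 1–2 points | 9.5%–23.6% |
| Controls 1 year younger, 0.2–0.3 per year | 6.0%–7.0% |
| Controls 2 years younger | 9.0%–12.5% |
| Controls 3 years younger | 13.5%–24.4% |
| Half siblings plus 2-year gap, same direction | 13.9%–25.4% |
| Half siblings plus 2-year gap, opposite directions (1.5 points, 0.3 per year) | 6.7% |

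The 25.4% corresponds to 1.5 points and 0.3 per year; with 2 points and 0.3 per year the rate is about 29% to 30%. The model adjusted for age, gender and parental education rejected in 4.4% to 5.4% of runs throughout. The simulated rates can fall slightly below the noncentral-F values because education adds to the outcome variance.

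**Masking.** Suppose both patient groups are truly 1.5 points worse than healthy children. Then λ = 8.333 and ANOVA power is 72.7%. An opposing bias of 0.4 leaves an apparent 1.1 points, λ = 4.481 and power 45.1%.

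**A second set of assumptions.** A single covariate correlated 0.2 to 0.4 with PSQI and shifted 0.3 to 0.8 SD in the healthy group gives bias of 0.2 × 0.3 = 0.06 to 0.4 × 0.8 = 0.32 SD. False-positive rates were 7% to 35% for ANOVA and 4% to 6% for ANCOVA. With a true cancer–healthy difference of 0.5 SD, the other-chronic group halfway, and an opposing imbalance, ANOVA power fell from about 60% to between 48% and 18%. ANCOVA kept 56% to 67%.

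**The case against.** Adjustment is not absent from the plan. Section 7 has a PSQI regression adjusted for age, gender and SES, its predictor list is open-ended, and Section 4.3.3 does not say that the adjustment must sit in the primary test. The list in Section 4.3.3 also includes disease type and status, which cannot enter a model with healthy children. An SAP, not shown here, could name group as a predictor. This stands as a qualification: group is not excluded from the regression, but nothing commits to it. It does not remove the conflict, because the protocol names the test for the primary contrast, and an SAP that followed Section 7 would inherit it.

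The sizes rest wholly on assumptions. That stands. In the mixed-control case the harm is modest, and rates above 20% need staff-only controls, a 3-year mean age gap, or two biases pointing the same way.

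The adjusted model's error rate is near 5% by construction, since the simulated data follow the fitted model. That also stands. Adjustment removes measured confounding only. It does not deal with the pairing of siblings with patients, or with a step in PSQI where the form passes from parent to child at about age 12. Nor can it separate illness from hospitalisation, because both patient groups are inpatients and the controls are not.

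**Conclusion.** The concern holds and should be fixed. The conflict between Sections 4.3.3 and 7 is in the text and depends on no assumption. Its consequence cannot be sized from the documents. Under the assumed inputs it runs from slight (6.4% to 8.8% false positives with half-sibling controls and balanced age) to serious (above 20% at the extremes), and imbalances in opposite directions can partly cancel. Both direction and size will be unknown until the group distributions are seen, which is why the model should be settled beforehand and not chosen between adjusted and unadjusted results afterwards.

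**What to change.** In Section 7, make the main group comparison a linear model (ANCOVA) of PSQI global score on group, age, gender and parental education. Report the adjusted cancer-minus-healthy and cancer-minus-other-chronic differences with 95% confidence intervals. Keep the one-way ANOVA as unadjusted support.

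As an optional addition, record who completed the PSQI and add informant in a sensitivity analysis. Keep it out of the main model, since it largely follows age and may partly follow illness.

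The cost is a wording change in Section 7 and, if the option is taken, one form field. The covariates are already collected. With education in four levels the model uses 1 + 1 + 3 = 5 further degrees of freedom, so the residual falls from 147 to 142. In the simulations the standard error of the cancer-minus-healthy difference ranged from about 2% smaller to 7% larger than under the ANOVA.
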